## PROTOCOL SUMMARY

Title:	Panoramic ECGi to guide Ablation of Non-Paroxysmal AF: Effect of Ibutilide on AF Source Location and Organization
Objective:	This prospective, multicenter observational study will examine the 1) Effect of Ibutilide on the number and size of the driver domains 2) Effect of ablation of Ibutilide-organized driver domains 3) Effect of PV isolation on driver domains
Design:	This is a prospective, multi-center, non-randomized, un-blinded, observational trial.
Enrollment:	
Eligible subjects will be consented for participation in the trial prior to undergoing AF ablation. Patients are considered eligible if they have
 
 
1. <math>\geq 18</math> years of age.
 
2.           
 
1) Symptomatic persistent AF refractory or intolerant to at least 1 class I or III antiarrhythmic medication Persistent AF - defined as Persistent: AF that is sustained <math>> 7</math> days. Episodes of AF which are terminated by electrical or pharmacologic cardioversion after <math>\geq 48</math> hours of AF, but prior to 7 days, should also be classified as persistent AF episodes.
 
2) Planned to undergo first catheter ablation procedure ( prior atrial flutter typical is allowed)
 
 
 
3. Ability to understand the requirements of the study and sign the informed consent form.
 
4. Willingness to adhere to study restrictions and comply with all post-procedural follow-up requirements
 
5. Projected lifespan greater than 1 year.
 
 
Patients will be excluded from the trial if:
 
 
1. They have baseline prolonged QT or renal failure precluding safe use of ibutilide
 
2. Rheumatic heart disease,
 
3. Current intra-cardiac thrombus,
 
4. History of MI or CABG within 6 weeks;
 
5. Class IV HF,
 
6. Unable to sign consent
 
7. Projected lifespan of <math>< 1</math> year
 
8. Women known to be pregnant or to have positive beta-HCG.
 
9. Participation in another study that would interfere with this study.
 
10. Unstable Angina
 
11. Recent cerebral ischemic events
 
12. Contraindication to anticoagulation
 
13. Prior history of polymorphic ventricular tachycardia or torsades de pointes
 
 
Patients are considered enrolled once consented. Patients who do not

	
undergo AF ablation within 90 days of enrolling will be considered to be screen failures.
 
Twenty subjects are expected to be enrolled in the study.

Clinical Sites:	
1. Mount Sinai Hospital, New York, NY  2. Homolka Hospital, Prague, Czech Republic

Time Course:	Expected duration of patient enrollment is approximately 8months to 1 year.
Subject Description:	Subjects will only be eligible for this study if they are $\geq$ 18 years of age and have a history of AF.
Primary Endpoints:	
 
1. Acute Procedural Outcome Analysis: after performing procedures on the 20 patients
 
2. Clinical Outcome Analysis - Freedom from recurrent At/AF at 12 months
 

Additional Endpoints:	
 
1. Effect of PV isolation on driver domains
 
2. Number/Size of drivers identified/ablated baseline
 
3. Percentage reduction of driver regions (site and size) after ibutilide
 
4. AF termination rate (to AT/SR)
 
5. Post-ablation inducibility of sustained AF (>5 mins) with isuprel
 
6. Post-ablation inducibility of AF with (>5mins) burst pacing
 
7. Total duration of RF ablation/ Fluro time/exposure/ procedure time
 

Follow-Up	
 
1) Post-Ablation blanking period = 3 months
 
2) AAD use during blanking: Any AAD is permitted, but should be stopped by 4 weeks post-procedure.
 
3) Any post-blanking AT or AF episode >30 seconds would be considered as a failure
 
4) Patients will undergo continuous 7-14 day ambulatory monitoring at 3, 6 and 12 months
 

Primary Analytical Analysis:	N/A
Secondary Analytical Analysis:	N/A
Principal Investigator:	[name] , M.D. Icahn School of Medicine at Mount Sinai [name]
Site, Monitoring, and Data Management Center	Electrophysiology Clinical Research Group Icahn School of Medicine at Mount Sinai [name]

## 2 STUDY OBJECTIVE

This prospective, multicenter observational study will examine the ability of ECGi mapping to

- 1) Effect of Ibutilide on the number and size of the driver domains
- 2) Effect of ablation of Ibutilide-organized driver domains
- 3) Effect of PV isolation on driver domains

We hypothesize that this approach will lead to successful arrhythmia control

## 3 INTRODUCTION, RATIONALE

Beyond PV isolation, ablation strategies for non-paroxysmal AF remain controversial although several types of targets have been proposed: non-PV triggers, continuous fragmented atrial electrograms, ganglionated plexi, and linear lesions. In STAR AF-2, PV isolation (PVI) alone resulted in successful maintenance of SR in only 59% of patients with persistent AF. This clearly reveals the need for establishing strategies to address non-PV sources of AF in non-paroxysmal AF. However, in the STAR AF-2 trial, after 18 months, the freedom from recurrent AF in patients assigned to PVI alone (59%) was not improved by the addition of either CFAE ablation (49%) or linear ablation (46%),  $p=0.15$ . Thus, beyond PV isolation, there is little consensus as to what additional lesion sets one should perform.

Localized driver domains perpetuating AF have been difficult to detect with conventional techniques because of the limits of sequential temporospatial mapping, intermittent firing, and, presumably, spatial meandering of rotor-like activity. However, panoramic biatrial AF mapping using a body surface array with 252 electrodes has been used to enable activation and phase-based analysis of body surface potentials. This noninvasive “ECG imaging”(ECGi) approach has been reported able to identify driver domains that, when targeted for ablation (along with PVI), can terminate AF. And most recently, the non-

randomized prospective multicenter AFACART study (8 centers, 118 patients) revealed that for persistent AF, the combination of PVI and ablation of driver domains identified by ECGi resulted in i) acute AF termination in 66% of patients, and ii) one-year freedom from recurrent atrial arrhythmias in 83%.

The efficacy of an ablation strategy of targeting these driver domains will require a number of clinical studies: both large randomized studies and smaller mechanistic studies. To this latter point, we propose conducting an exploratory study of the use of panoramic ECGi in non-paroxysmal patients, in which the effect of pharmacological organization of driver domains will be evaluated, by the administration of progressive doses of Ibutilide.

## **4 DEVICES AND PROCEDURES**

### **4.1 CardioInsight ECGi Mapping System**

The CardioInsight mapping system is a noninvasive, single beat cardiac arrhythmia mapping system that provides 3D electroanatomic maps of the heart. It combines body surface potential measurements with cardiac anatomy to generate panoramic, bi-atrial or bi-ventricular 3D electroanatomic maps. The components include a cart, workstation, mapping amplifier, isolation transformer, monitor, manual, connection cables and a Sensor Array. The CardioInsight mapping system has market approval in the U.S.

### **4.2 Ablation Catheters**

The AF ablation procedure will be performed using any of the following marketed catheters: (Note: the catheters listed below are FDA approved for the treatment of paroxysmal atrial fibrillation but not persistent.)

- **Biosense Thermocool SF**
- **Biosense Smart Touch SF (STSF)**

## 5 SCHEDULE OF TREATMENT AND TESTS

TABLE 1: SCHEDULE OF TREATMENTS AND TESTS:

	Baseline	Procedure	Discharge	3 months	6 months	12 months
Type of visit	Office	Hospital		Telephone Event Monitor	Telephone Event Monitor	Telephone Event Monitor
Informed Consent	X					
Brief History & Physical	X					
Blood Laboratory Testing: CBC, Electrolytes, BUN/Creatinine, BNP, INR, LFTs	X					
TTE	X					
CT	X					
EKG	X					
Medications	X	X	X	X	X	X
AFEQT	X					X
Holter Monitoring				X	X	X
Adverse Events		X	X	X	X	X

## 6 ENDPOINTS

### 6.1 Primary Endpoint

Primary Endpoints:	1. Acute Procedural Outcome Analysis: after performing procedures on the 20 patients 2. Clinical Outcome Analysis - Freedom from recurrent At/AF at 12 months
Additional Endpoints:	1. Effect of PV isolation on driver domains 2. Number/Size of drivers identified/ablated baseline 3. Percentage reduction of driver regions (site and size) after ibutilide 4. AF termination rate (to AT/SR) 5. Post-ablation inducibility of sustained AF (>5 mins) with isuprel 6. Post-ablation inducibility of AF with (>5mins) burst pacing 7. Total duration of RF ablation/ Fluro time/exposure/ procedure time

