#### Other mapping and protocols

Isoprenaline challenge for trigger mapping or for induction of sustained atrial fibrillation

- The infusion can be used for doses as high at 30mcg/kg/min and should be continued for 10-30 minutes to truly assess the effect of isoprenaline. Trigger mapping requires the operators to use at least 20 mcg/kg/min or maximum tolerated dose for 10-20 minutes. When isoprenaline is used to sustain AF in cases where AF induced by pacing is nonsustained then lower doses can be used – 2-4 mcg/kg/min

AF induction and cardioversion- Induce atrial fibrillation by rapid pacing in the atrium. Once sustained AF is noted- then perform DCCV and wait to see if triggers are seen inducing atrial fibrillation.

- **Presenting rhythm- Sinus- Induce AF – is sustained >15 mins**
  - Map sinus acquired first and then Map induceAF will be acquired
- **Presenting rhythm- Atrial fibrillation**
  - Map spontAF will be acquired  
PV isolation is initially completed with standard approach
  - If AF persists then

- Progressive doses of Ibutilide should be administered (0.25mg, then 0.25mg, then 0.5mg) and repeat ECGi mapping (MapIbutilide0.25, MapIbutilide0.50 & MapIbutilide1.00) should be performed. If the rhythm organizes to atrial tachycardia this will be ablated and if rhythm converts to sinus – then procedure is deemed complete.

If still in AF, Driver regions are targeted  
(Right and left atria)

Prior to ablation- LAA and RAA cycle length are to be measured over 10 beats

Ablation of drivers can be initiated in chamber with faster CL or with greater number of identified drivers. Drivers can be addressed in order of importance as suggested by maps.

Periodic reassessment of TCL in LAA and RAA to be done to help direct operator to chamber of interest- e.g. if there is significant gradient between RAA and LAA such that RAA is faster then drivers can be pursued in RAA prior to completion of all driver regions of LA

All drivers are to be sequentially ablated; if rhythm is still not organized then ablation sites are visited again to ensure adequate ablation. If AF persists, ECGi mapping should be repeated (MapRe1,2.) and additional driver regions can be targeted

- **Ibutilide Dosing Guidelines**

1. Patients <60 kg – Ibutilide dosing is limited to a maximum dose of 0.50
2. Patients >60 kg are allowed to receive full dosing of ibutilide up to 1.0mg

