## 17 DATA ANALYSIS

Baseline clinical characteristics (e.g. age, gender, renal function) and procedural characteristics (e.g. surface intracardiac electrogram, and imaging findings) of the patients will be collected and analyzed. All continuous variables will be performed as the mean  $\pm$  standard deviation, and all categorical variables as a percentage of the total study population.

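### The ibutilide driver endpoint has no stated reference map or dose step, and the only AF map named before ibutilide is placed before PV isolation

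*Combined protocol and SAP*

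**What the plan says.** The study title includes "Effect of Ibutilide on AF Source Location and Organization", and the first objective in section 2 is "Effect of Ibutilide on the number and size of the driver domains". The matching additional endpoint in section 6.1 is "Percentage reduction of driver regions (site and size) after ibutilide". It names no reference map, dose step or analysis set. The same list has a separate endpoint, "Effect of PV isolation on driver domains", and one for the number and size of drivers at baseline.

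The sequence of maps is in section 10.3, under Other mapping and protocols:

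- Patients presenting in sinus rhythm: "Map sinus acquired first and then Map" induceAF.
- Patients presenting in AF: Map spontAF, followed by "PV isolation is initially completed with standard approach".
- If AF persists: "Progressive doses of Ibutilide should be administered (0.25mg, then 0.25mg, then 0.5mg) and repeat ECGi mapping", giving maps at cumulative doses of 0.25, 0.50 and 1.00 mg.
- Organization to atrial tachycardia (AT) leads to ablation of the AT, and conversion to sinus rhythm ends the procedure.

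The Ibutilide Dosing Guidelines stop the infusion when AF terminates, cap the total dose below 60 kg, and withhold further doses above a QTc limit.

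On analysis, section 17 says "All continuous variables will be performed as the mean" with standard deviation, and percentages for categorical variables. It does not mention paired change, a reference map, or patients with no later map.

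**The concern.** A percentage reduction needs a starting value. Followed as written, section 10.3 offers one AF map before ibutilide, and PVI takes place between that map and the first dose. A reduction from that map to an ibutilide map includes whatever PVI did to the drivers, yet it would be reported as a reduction after ibutilide. Because the ibutilide effect is in the title and is Objective 1, a reader would naturally credit the drug with the whole change.

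There is a second, smaller issue. Patients who convert or organize have no AF driver map from that point on, so later-dose summaries describe only those still in AF. A bare mean and SD does not show how many patients that is or why the others are absent.

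**Working it through.** The plan has no figure of its own to reproduce. The sample size of 20 rests on feasibility (section 8), and no expected reduction, SD or PVI effect is given.

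**Step 1: order of the maps.** For patients presenting in AF, section 10.3 gives this order:

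1. Map spontAF
2. PVI
3. Ibutilide 0.25 mg and its map
4. Ibutilide to 0.50 mg and its map
5. Ibutilide to 1.00 mg and its map

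No map is named between items 2 and 3. For patients presenting in sinus rhythm, Map induceAF is named, but the PVI line is set out under the AF-presenting branch. That this map also precedes PVI is an inference from PVI being described as done initially. The only named AF maps that could supply the baseline driver count in section 6.1 are Map spontAF and Map induceAF.

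**Step 2: what a pre-PVI reference measures.** Let D be the driver regions on the baseline map, q the fraction removed by PVI, and r the fraction of the remainder removed by ibutilide. Then:

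- after PVI: D(1 − q)
- after ibutilide: D(1 − q)(1 − r)
- reduction from the pre-PVI map: 1 − (1 − q)(1 − r)
- reduction from a post-PVI map: r

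The values of q and r are assumed, as is the proportional action of ibutilide on what PVI leaves.

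| PVI removes (q) | Reading if ibutilide removes 0% | Reading if ibutilide removes 40% |
|---|---|---|
| 10% | 1 − 0.9 × 1.0 = 10% | 1 − 0.9 × 0.6 = 46% |
| 20% | 1 − 0.8 × 1.0 = 20% | 1 − 0.8 × 0.6 = 52% |
| 30% | 1 − 0.7 × 1.0 = 30% | 1 − 0.7 × 0.6 = 58% |

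A post-PVI reference returns 0% and 40% in every row. If PVI removes no drivers (q = 0), the two references agree.

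**Step 3: comparisons between doses.** All three ibutilide maps follow PVI. The ratio of regions at a later dose to those at the first dose in the same patient is D(1 − q)(1 − r_later) / [D(1 − q)(1 − r_first)] = (1 − r_later) / (1 − r_first). Both D and q cancel, so PVI does not enter. This contrast shows only the change after the first dose step, not the full effect against no drug.

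**Step 4: who has a map at each dose.** Four routes shorten the series: conversion to sinus rhythm, organization to AT, the weight cap and the QTc rule. The first two are themselves responses to treatment. Section 6.1 lists an AF termination rate but specifies no breakdown by dose. The documents give no exit rates and nothing on how exit relates to driver reduction, so the effect of these exits on the mean cannot be calculated.

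**The case against.** The strongest reply is that a post-PVI map may well be intended. Objective 3 and the PVI endpoint cannot be met without one, so the gap may be an unnamed map and not a confounded endpoint. That stands as far as it goes. However, the map is not in the procedural sequence, and nothing ties it to the ibutilide endpoint, so the reference remains open.

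A reader might infer that the endpoint can never be read as an ibutilide effect. The documents do not support that: a post-PVI map would resolve the problem, and within-patient contrasts between doses are already free of PVI mixing.

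A reader might also infer that later-dose means understate the ibutilide effect because responders leave. That does not follow either. If exit is unrelated to the size of the reduction, no such bias arises, and the documents do not show which case applies. A mean among patients still in AF is also a legitimate description of those whose drivers are then targeted. It only needs to be labelled that way.

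Finally, this is an additional endpoint in an exploratory, descriptive study of 20 patients. That limits what should be asked for, but a preliminary estimate still needs a defined contrast.

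**Conclusion.** The point holds as a gap in definition with a real consequence. Measured from the baseline map that the protocol names, the endpoint combines the effects of PVI and ibutilide. Under the assumed 10-30% removal by PVI, it would read 10-30% with an inactive drug and 46-58% when the true effect is 40%, an excess of 6 to 18 points in the latter case. The algebra depends only on the map order; the size depends wholly on assumed inputs. The order is explicit for Map spontAF and inferred for Map induceAF.

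No direction or size can be given for any selection effect from patients leaving AF. That part is a reporting need, not a demonstrated bias.

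**What to change.** Amend sections 6 and 17 and reconcile them with section 10.3:

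- **Reference map.** State whether a post-PVI, pre-ibutilide map is acquired. If it is, name it as the reference for the ibutilide endpoint. If it is not, label the change from the pre-PVI map as the combined effect of PVI and ibutilide, and limit ibutilide-specific statements to changes between dose steps in the same patient.
- **Contrast.** Report within-patient paired change in driver number and size with a 95% CI, and state which dose-step map is used.
- **Counts.** At each dose, report how many patients were mapped, converted to sinus rhythm, organized to AT, or stopped for weight or QTc. Describe later-dose means as applying to patients still in AF.

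The cost is wording, a little more analysis, and recording of rhythm and reason for stopping at each dose if the case report form does not already hold them; its fields are not shown in the documents. If no post-PVI map exists, the label becomes less favourable to the ibutilide claim. No dose or clinical rule needs to change for this.

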## **8 SAMPLE SIZE**

[figure not shown]
This safety and efficacy study will enroll 20 patients across 1US centers and 1 OUS center. This number has been determined on the basis of study feasibility and not by statistical means. This is a feasibility study of the mapping system (ECGi) performance in which the sample size of the clinical investigation is intended to provide preliminary estimates of safety and performance.

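### Additional endpoints 5 and 6: some patients may have no post-ablation induction test, and an inducible percentage reported alone over all patients would treat them as non-inducible

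*Combined protocol and SAP*

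**What the plan says.** Section 6.1 lists seven additional endpoints. The fifth is "Post-ablation inducibility of sustained AF (>5 mins) with isuprel" and the sixth is "Post-ablation inducibility of AF with (>5mins) burst pacing". Both are yes/no results of a test, so a patient who is not tested has no result.

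Section 10.3, under Other mapping and protocols, describes the methods: an "Isoprenaline challenge for trigger mapping or for induction of sustained atrial fibrillation", in permissive wording, and, for pacing, "Induce atrial fibrillation by rapid pacing in the atrium", followed by cardioversion and a watch for triggers. Neither is tied to the end of ablation, and nothing says which patients are tested. In the same section, if ibutilide converts the rhythm to sinus, "then procedure is deemed complete". For patients still in AF after repeat driver ablation, neither cardioversion nor testing is stated.

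Section 17 is a single short paragraph. Its only denominator rule is to report "all categorical variables as a percentage of the total study population". It names neither endpoint and does not mention tests not done. Section 8 gives the planned number: "This safety and efficacy study will enroll 20 patients".

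**The concern.** A fixed denominator of all patients suits a characteristic known for everyone. It suits a test result less well when the test may be missing. An untested patient cannot enter the numerator but stays in the denominator, so the inducible percentage falls without any evidence that the patient was non-inducible. Someone who left the laboratory in AF and untested would then count the same as someone tested and not inducible.

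At stake is the reading of two descriptive endpoints in a study meant to give preliminary estimates. No hypothesis test, success threshold or sample-size calculation depends on them.

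**Working it through.** **Inputs.** N = 20 (Section 8). The denominator is the total study population (Section 17). The number untested (u) and the number inducible (x) are not in the documents. They are assumed below, with u from 0 to 10 and between 22% and 50% of tested patients inducible. The plan states no inducibility rate, so there is no figure of its own to reproduce.

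**Formulas.** The number tested is n = N − u.

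- Inducible share over all patients: x/N.
- Tested-patient rate: x/n. Hence x/N = (x/n) × (N − u)/N, a relative shortfall of u/N.
- All-patient bounds: x/N if no untested patient is inducible, to (x + u)/N if all are. The width is u/N, so one untested patient of 20 adds 1/20 = 5 percentage points.

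**Results for N = 20** (exact Clopper-Pearson 95% intervals for x/n):

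| u (assumed) | x (assumed) | x/20 | x/n (95% CI) | Bounds |
|---|---|---|---|---|
| 0 | 5 | 25% | 5/20 = 25% (8.7–49.1) | 25–25% |
| 2 | 4 | 20% | 4/18 = 22.2% (6.4–47.6) | 20–30% |
| 4 | 4 | 20% | 4/16 = 25.0% (7.3–52.4) | 20–40% |
| 5 | 6 | 30% | 6/15 = 40.0% (16.3–67.7) | 30–55% |
| 8 | 6 | 30% | 6/12 = 50.0% (21.1–78.9) | 30–70% |
| 10 | 5 | 25% | 5/10 = 50.0% (18.7–81.3) | 25–75% |

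The figure over 20 always equals the lower bound. With u = 0 the two rules agree.

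**Opposite direction.** If the non-inducible share is reported over N, it is (N − u − x)/N, which implies an inducible rate of (x + u)/N, the upper bound. With u = 4 and x = 4 this is 12/20 = 60% non-inducible, against 12/16 = 75% among those tested. The untested now count as inducible.

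**Which N.** Section 17 does not define the total study population. Section 9 counts patients as enrolled once consented and treats those not ablated within 90 days as screen failures. If such patients were kept in N, the dilution would be larger.

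**The case against.** The strongest reply is that Section 17 is a general format for summary statistics and does not make inducibility a two-level variable. A table of inducible, non-inducible and not tested, each over 20, obeys the rule literally and miscounts nobody. This stands: the problem arises only if one percentage is reported alone.

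Second, listing both tests as endpoints with no subset suggests that everyone treated should have them, and declaring the procedure complete may mean only that no more ablation is needed. That is a fair reading, and complete testing would remove the effect. But nothing requires the test, so missing results are foreseeable.

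Third, the shifts are mostly within sampling error. The exact 95% interval is 5.7–43.7% for 4/20 and 11.9–54.3% for 6/20, and each contains the matching tested-patient rates above. Only the u = 10 row falls just outside (50% against 8.7–49.1% for 5/20). This limits the importance, but the shift is avoidable and random error is not.

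Fourth, the root gap is that Section 10.3 does not say who is tested and when. That is true, and a reporting rule does not close it. The rule does make the gap visible without imposing re-induction on patients.

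A reader might also take the cited ECGi-guided ablation study in Section 3, with "acute AF termination in 66% of patients", and infer that (1 − 0.66) × 20 = 6.8, or about 7 patients, would go untested. The documents do not support this. That rate comes from a strategy without this study's ibutilide step; nothing says patients still in AF go untested; and the sum treats ibutilide converters as all tested, although they are the group whose procedure is explicitly declared over.

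**Conclusion.** The point holds in conditional form and is minor. Untested patients are foreseeable from Section 10.3, and the only written denominator does not separate them from tested ones. If the inducible percentage alone is reported over N, it is the lowest all-patient rate compatible with the data; it may equal the true rate or understate it. With 20 patients it falls short of the tested-patient rate by a relative u/20 (10% for u = 2, 40% for u = 8), and the bounds are 5 percentage points wide per untested patient.

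This rests on one assumption, that at least one patient is untested. How many is unknown, and with none the effect is zero.

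A reader might infer that the plan instructs untested patients to be scored non-inducible, or that any error must favour the procedure. Neither follows. The documents contain no such instruction, and they do not fix which level is reported; reporting the non-inducible share over N would count against the procedure. The primary endpoints and the sample size are untouched.

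**What to change.** Add one or two sentences to Section 17. For endpoints 5 and 6 separately:

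- report inducible/tested (x/n), and state that it describes tested patients only;
- give the number not tested, by reason (converted on ibutilide, AF ended during PV isolation, still in AF at the end, not attempted);
- give the bounds x/N to (x + u)/N, with N defined as all treated patients.

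Add one CRF field per test: done yes/no, with the reason if not. It is best in place before enrolment, because reasons are more reliable when recorded at the procedure. No procedure is added, and patients who convert on ibutilide need not be re-induced.

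The cost is a smaller denominator and a wider interval (for example 5/10: 18.7–81.3%), from a tested group that may be selected, so x/n can differ from the all-patient rate. The bounds show how far untested patients could move that rate.
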